## **List of Abbreviations**

Abbreviation	Definition			
AE	Adverse event			
ALI	Acute lung injury			
ARDS Acute Respiratory Distress Syndrome				
CAS Chemical abstract services				
CR	Child-resistant Child-resistant			
CRF	Case Report Form			
DPG	Diphosphoglycerate			
ECG	Electrocardiogram			
ECMO	Extracorporeal membrane oxygenation			
eIND	Exempt investigational new drug			
EMR	Electronic medical record			
ESLD	End -stage lung disease			
FDA	Food and drug administration			
FEMA	Flavor and Extract Manufacturers Association of the United States			
FiO 2	Fraction of inspired oxygen			
GBT	Global Blood Therapeutics			
GMP	Good manufacturing practice			
GRAS	Generally recognized as safe			
Hb	Hemoglobin			
HbF	Fetal hemoglobin			
Hb-O 2	Hemoglobin-oxygen			
HbS	Sickle hemoglobin			
Hct	Hematocrit			
HR	Heart rate			
ICU	Intensive care unit			
IDS	Investigational drug services			
IID	Inactive Ingredients Database			
INN	International nonproprietary name			
IPF	Idiopathic pulmonary fibrosis			
LAR	Legally Authorized Representative			
LPM	Liters per minute			
NYHA	New York Heart Association Functional Classification			
O 2	Oxygen			
OEC	Oxygen equilibrium curve(s)			
ODC	oxygen dissociation curve			
p20	Partial pressure of oxygen resulting in 20% saturation of hemoglobin with oxygen			
p50	Partial pressure of oxygen resulting in 50% saturation of hemoglobin with oxygen			

PaCO 2	Partial pressure of carbon dioxide
PaO 2	Partial pressure of oxygen
PD	Pharmacodynamics
PK	Pharmacokinetics
PO 2	Partial pressure of oxygen
PP	Polypropylene
RBC	Red blood cells
Abbreviation	Definition
RN	Registered nurse
SAE	Serious Adverse event
SaO 2	Oxygen saturation
SCD	Sickle cell disease
S/F	SpO 2 /FiO 2 ; ratio of inspired oxygen needed to obtain a specific oxygen saturation
SOC	Standard of care
SpO 2	Oxygen saturation
SS	Sickle cell
SSRBC	Sickle cell red blood cell
STRT	Study team respiratory therapist
TEAE	Treatment-emergent adverse event
ULN	Upper limit of normal
VOC	Vaso-occlusive crisis

### 1 Introduction

This document is a protocol for a human research study. This study is to be conducted according to US and international standards of Good Clinical Practice (FDA Title 21 part 312 and International Conference on Harmonization guidelines), applicable government regulations and Institutional research policies and procedures.

Voxelotor (GBT440) is a small molecule inhibitor of sickle hemoglobin (HbS) polymerization which allosterically modifies hemoglobin-oxygen (Hb-O2) affinity that was developed by Global Blood Therapeutics (GBT) and is FDA-approved for the treatment of sickle cell disease in adults and pediatric patients 12 years of age and older.

## 1.2 Investigational Agent

# PHYSICAL, CHEMICAL, AND PHARMACEUTICAL PROPERTIES AND FORMULATION

#### **Molecular Structure**

Chemical Name: 2-Hydroxy-6-((2-(1-isopropyl-1H-pyrazol-5-yl)pyridin-3-yl)

methoxy)benzaldehyde Company Code: GBT440 Chemical Abstracts Service (CAS) registry number: 1446321-46-5 International Nonproprietary Name (INN): Voxelotor

#### Structure:

Molecular Formula: C19H19N3O3

Molecular Weight: 337.4

Physical Description Voxelotor is a synthetic small molecule bearing the chemical name 2-hydroxy-6-((2-(1- isopropyl-1H-pyrazol-5-yl)pyridin-3-yl) methoxy)benzaldehyde. The chemical formula is C19H19N3O3 and the molecular weight is 337.4.

Voxelotor is a white-to-yellow-to-beige compound in crystalline Form II of GBT440 free base. It is non-hygroscopic. It is highly soluble in common organic solvents such as acetone and toluene and insoluble in water (approximately 0.03 mg/mL). Voxelotor drug substance is manufactured in accordance with Good Manufacturing Practice (GMP). The chemistry used in the production of voxelotor drug substance is well established. The manufacturing process uses equipment commonly available in the industry.

#### **Nonclinical Pharmacology**

The pharmacology program established the mechanism of action by testing effects of voxelotor on HbS and by assessing the benefit on downstream inhibition of HbS polymerization both in vitro and in animal disease models

#### **Primary Pharmacology**

The in vitro primary pharmacology studies defined the mechanism of action of voxelotor and the in vivo studies determined the relationship between voxelotor blood concentration and ex vivo effects on Hb-O2 affinity as well as its physiologic and pathologic effects in a sickle cell mouse model. In addition, using a voxelotor analogue in C57BL/6 and sickle cell disease (SCD) mice, these studies also addressed its ability to preserve oxygen (O2) extraction in various organs, including the brain, ultimately translating to improved survival. Findings from the primary pharmacological studies demonstrated that voxelotor has the ability to:

- ° bind specifically to Hb,
- o partition to red blood cells (RBCs),
- ° increase Hb-O2 affinity and stabilize the oxyHb state,
- ° inhibit HbS polymerization,
- o improve RBC rheology in human sickle cell (SS) blood,
- ° exhibit ex vivo anti sickling activity in a SCD mouse model,

- o increase RBC half-life and reduce reticulocyte counts in a SCD mouse model,
- o in addition, a voxelotor analogue preserved O2 extraction in various organs and improved brain oxygenation and survival in both normal and SCD mice.

Furthermore, these studies showed that voxelotor-modified Hb can release O2 at lower pH, indicating that voxelotor binding to Hb does not interfere with the ability of Hb to deliver and offload O2 to metabolically active tissues.

#### **Binding of Voxelotor to Hemoglobin**

[figure not shown]
Crystallography studies of cocrystals of carbon monoxide-liganded Hb and voxelotor show that:

- ° Voxelotor binds to the N-terminal valine residue of an α chain; a single GBT440 molecule binding per Hb tetramer in a 1:1 stoichiometry (Study PRC-18-048; Oksenberg D, 2016; Metcalf B, 2017).²
- ° The voxelotor binding site is distant from heme pockets and therefore does not directly prevent release of O2 from Hb (Patel M, 2014, data on file). Thus, voxelotor increases Hb-O2 affinity without sterically blocking the release of O2.

#### **Effect of Voxelotor on Hemoglobin-Oxygen Affinity**

The oxygen equilibrium curve (OEC) for whole blood relates the extent of Hb-O2 saturation to the partial pressure of oxygen (pO2) and measures the binding affinity of O2 to Hb. Blood OECs allow for the measurement of the partial pressure of oxygen resulting in 20% saturation of hemoglobin with oxygen (p20) or partial pressure of oxygen resulting in 50% saturation of hemoglobin with oxygen (p50) values, which are the pO2 at which Hb is 20% or 50% saturated with O2, respectively. Measurement of OECs using whole blood from patients with SCD (Figure 2) shows a dose-dependent left-shift of the OEC and decrease in p50 and p20 values upon addition of voxelotor (Figure 1).

Figure 1: Effect of Voxelotor on Hemoglobin-Oxygen Affinity in Whole Blood from Patients with SCD

Abbreviations: O2, oxygen; pO2, partial pressure of oxygen.

Source: Study PRC-14-027-R

#### Stabilization of Hemoglobin in a High Oxygen Affinity State by Voxelotor

Hb exists in both a R and a T state with high and low affinity for O2, respectively. Cooperativity arises from a shift in the population from the low affinity T structure to the high affinity R structure with increasing O2 affinity (Eaton WA, 1999). Using the oxygen dissociation assay (), voxelotor was shown to effectively maintain a high percent of Hb in the oxyhemoglobin conformation (associated with the R state) under hypoxic conditions (Study PRC-14-033-R; Patel MP, 2018) whilst maintaining the ability of O2 to offload from Hb.

# Voxelotor-modified Hb maintains the physiological mechanisms required for tissue O2 extraction

The ability of H+ ions and 2,3 diphosphoglycerate (DPG) to reduce Hb-O2 affinity are 2 of the key physiologic mechanisms that drive O2 offloading to metabolically active tissues. In vitro studies with voxelotor modified Hb and whole blood in the presence of H+ ions or DPG showed the expected increase in dissociation of O2. Therefore, physiologic mechanisms of augmenting tissue O2 extraction, including the Bohr effect and 2,3 DPG binding (Studies PRC-14-029-R and PRC-18-046) are preserved with voxelotor modified Hb.

#### 1.3 Preclinical Data

# Prevention of Sickle Hemoglobin Polymerization and Red Blood Cell Sickling In Vitro The intracellular polymerization of HbS upon deoxygenation is the primary pathogenic event in

SCD (Noguchi CT, 1981). Delaying HbS polymerization long enough may prevent the RBCs from damage and sickling while transiting hypoxic tissue capillaries in patients with SCD. Therefore, the ability of voxelotor to delay HbS polymerization in vitro was evaluated (Study PRC-14-040-R). Voxelotor was shown to delay polymerization in a dose-dependent manner and mimicked the profile of polymerization delay afforded by the presence of 20% to 30% fetal hemoglobin (HbF) (Table 1).

Table 1: Delay of Sickle Hemoglobin Polymerization by Voxelotor, and Fetal Hemoglobin

% Inhibitor a	HbF ΔDT (min)	GBT440-HbS ADT (min)
20	8.8	10
30	13.1	14

Abbreviations: ΔDT, delay time (Delay time of Hb mixture – Delay time of HbS alone); HbF, fetal hemoglobin; min, minutes.

These data indicate that like HbF, voxelotor is a potent inhibitor of in vitro HbS polymerization and suggest that by delaying HbS polymerization, voxelotor may prevent RBC damage and sickling from patients with SCD.

[figure not shown]
This decrease in polymerization causes a corresponding dose dependent decrease in the number of sickled RBCs (SS RBCs) in blood from patients with sickle cell disease under variable hypoxic conditions. The therapeutic target of 30% modification is sufficient to prevent in vitro

 $^{a}$  Inhibitor is HbF, or GBT440-HbS added to unmodified HbS. Final concentration of Hb = 50  $\mu$ M. Source: Study PRC-14-040-R.

sickling of SS RBCs at an O2 tension typical of tissue capillaries (40 mmHg) (Study PRC-14-042 R).

Voxelotor dose-dependently reduced the number of sickled RBCs under hypoxic conditions (pO2 of < 40 mmHg) (Figure 3), mimicking O2 tensions in tissue capillaries. Effect on Sickle Blood Viscosity and Deformability In Vitro Furthermore, by inhibiting HbS polymerization, voxelotor improves SS RBC deformability and decreases SS blood hyperviscosity in vitro under hypoxic conditions (Studies PRC-14-044-R and PRC-14-031-R, Dufu K, 2018). The effect of voxelotor on SCD blood viscosity was evaluated under deoxygenated conditions and compared to untreated SCD blood and blood from healthy subjects. Voxelotor reduced the viscosity of the deoxygenated SS blood when compared to untreated deoxygenated SCD blood (Figure 4A) and the viscosity of deoxygenated SCD blood improves with increasing voxelotor concentrations (Figure 2)

Figure 2: Voxelotor Prevents Red Blood Cell Sickling

Abbreviations: RBC, red blood cell; pO2, partial pressure of oxygen. Source: Study PRC-14-042-R.

#### Effect on Sickle Blood Viscosity and Deformability In Vitro

Furthermore, by inhibiting HbS polymerization, voxelotor improves SS RBC deformability and decreases SS blood hyperviscosity in vitro under hypoxic conditions (Studies PRC-14-044-R and PRC-14-031-R, Dufu K, 2018). The effect of voxelotor on SCD blood viscosity was evaluated under deoxygenated conditions and compared to untreated SCD blood and blood from healthy subjects.

Voxelotor reduced the viscosity of the deoxygenated SS blood when compared to untreated deoxygenated SCD blood (Figure 3A) and the viscosity of deoxygenated SCD blood improves with increasing voxelotor concentrations (Figure 3B).

[figure not shown]

Figure 3: Voxelotor Reduces the Hyperviscosity Observed in SCD Blood

AA — Normal blood with HbA; SS — Blood from sickle cell patients.¶

Source: Study PRC-14-044-R.

Decreased RBC deformability and increased RBC rigidity in SCD have significant positive implications for microcirculatory blood flow and prevention of end-organ damage. Deformability experiments also showed that voxelotor restored deformability of human SS RBC under hypoxic conditions (Study PRC-14-031-R). In vitro results indicate that voxelotor reduces the blood hyperviscosity associated with deoxygenation of HbS. Since the viscosity of SCD blood under hypoxic conditions is primarily determined by polymer load, these data suggest that voxelotor decreased SS blood viscosity by reducing intracellular polymer load resulting from HbS polymerization. Consequently, this suggests a potential to improve the blood flow in the microcirculation, thus improving O2 delivery to peripheral tissues. As viscosity increases with hematocrit (Hct), and because sickle blood has an increased viscosity compared to normal blood for any given Hct, these results are important in supporting the potential for voxelotor to increase Hct and Hb in SCD patients without causing a clinically adverse worsening in blood viscosity.

#### 1.4 Clinical Data to Date

#### **GBT Sponsored Clinical Studies**

As of 05 November 2020, 28 clinical development studies (8 studies in SCD, 2 studies in idiopathic pulmonary fibrosis (IPF), 17 clinical pharmacology studies, and 1 study of healthy participants under hypoxic conditions, Study GBT440-0111) have enrolled an estimated 939 participants who have been exposed to at least 1 dose of voxelotor. An additional 176 clinical study participants received placebo in the voxelotor development program. The 939 participants who received voxelotor consist of:

- 430 participants with SCD: 276 adults and 154 pediatric participants (this includes participants enrolled in the expanded access program)
- ° 404 healthy participants from the 17 clinical pharmacology studies (including participants with severe renal impairment [not on dialysis] and participants with hepatic impairment)
- 62 healthy participants enrolled in studies other than clinical pharmacology (GBT440-001 and GBT440-0111)
- 43 adult participants with IPF

#### 1.5 Dose Rationale and Risk/Benefits

Based on the clinical studies safety data evaluated to date, voxelotor has an acceptable safety profile and has been well tolerated in adult and pediatric participants (aged 4 to < 18 years) with SCD. The most common adverse reactions in participants with SCD  $\geq$  12 years old were diarrhea, abdominal pain, nausea, rash, and pyrexia. Other clinically relevant and less frequent adverse reactions included drug hypersensitivity (< 1%). There were no reported events of anaphylaxis or anaphylactoid reactions. The majority of Treatment Emergent Adverse Event (TEAEs) were Grade1 to Grade 2 severity, clinically manageable, reversible or resolved. The TEAE profile of voxelotor for pediatric participants with SCD aged  $\geq$  4 to 11 years at a dose of 1500 mg or equivalent weight-based dosing is acceptable with no new safety observations and is consistent with the data for adults and adolescent participants.

Overall, the safety profile was similar between adults and pediatric participants aged  $\geq 4$  years and between participants who were or were not receiving hydroxyurea concomitantly.

In the pivotal Study GBT440-031, over the 72-week treatment period, there was a trend towards a lower overall incidence of vaso-occulsive crisis (VOC) with numerically fewer VOC events in the voxelotor groups compared to the placebo group, although the differences did not reach statistical significance. No increase in the incidence of VOC was observed following discontinuation of voxelotor (up to 28 days after the last dose of study drug).

No clinical safety concerns consistent with inadequate tissue oxygenation were identified in the voxelotor clinical development program, including in SCD study participants.

The most common side effects of voxelotor include:

- Headache
- Diarrhea
- Stomach (abdominal) pain
- Nausea
- Fatigue (Tiredness)
- Rash
- Fever

Less common, but severe, side effects of voxelotor include:

- Pulmonary embolism
- Hypersensitivity reactions (occurring in <1% of patients treated), including the following symptoms:
  - ° Generalized rash
  - Urticaria (hives)
  - Mild shortness of breath
  - Mild facial swelling
  - ° Eosinophilia (an increase in one of the white blood cells in your blood called eosinophils)

As voxelotor increases the binding of oxygen to hemoglobin (providing the treatment effect of increased SpO2 for a given pO2), we will monitor for the possibility of inadequate oxygen being off-loaded to the tissues by measuring venous blood gases for evidence of metabolic acidosis

from tissue beds and tracking renal function as a reflection of adequacy of tissue oxygen during administration of Voxelotor.

There may also be risks, discomforts, drug interactions, or side effects that are not yet known.

# 2 Study Objectives

The purpose of the study is to evaluate the efficacy of voxelotor for increasing oxygen saturation in patients with hypoxemia. Specifically, the SpO2/FiO2 ratio will be compared before and after voxelotor use at rest and during exercise (ambulatory patients only).

#### **Primary study objective**

To evaluate the efficacy of voxelotor for increasing oxygen saturation in patients with hypoxic hypoxemia as a result of end-stage lung disease or acute lung injury.

#### Secondary study objective

To evaluate the efficacy of voxelotor on allowing de-escalation of supplemental oxygen support.

**Exploratory endpoints**: Pre and post Voxelotor use compare

- ° FiO2 requirements
- Oxygen delivery modality
- ° Combined end-point of de-escalation of FiO2 and/or oxygen delivery modality
- ° Nadir SpO2
- Oxygen flow
- Healthcare utilization
- Dyspnea scale

# 3 Study Design

## 3.1 General Design

Following a screening period and observation that clinical status is stable and requiring substantial oxygen support for 48 hours, subjects with decompensation of ESLD or ALI with hypoxemia, will be approached for informed consent. The nature of the risks and benefits associated with participation in the study will be explained to all potential study subjects or legally authorized representative (LAR). Written informed consent must be obtained before the subject can begin any screening procedures that are not considered standard patient care.

**Physiological data:** Physiological data at screening, baseline, study day 1-5, and up to two days post voxelotor administration will be recorded from standard of care with the only exception being SpO2/FiO2 (S/F) ratio measurements, which will be obtained at the same intervals but by the qualified and delegated study staff or medical team through the use of an FiO2 weaning maneuver.

Physiological measures to be recorded are detailed on the Schedule of Activities table 2.

**FiO2** Weaning Maneuver: The process of titrating FiO2 down slowly until the study patient's SpO2 measurement is approximately 88%. This will provide the study team with values for an S/F ratio that more closely represents the transition to the steepest part of the oxygen dissociation curve (ODC). Measurements that represent this transition on the ODC will allow for more precise comparison and provide more accurate trending data. Once completed, the oxygen delivery system will be titrated back to achieve SpO2 goals prescribed by the medical team.

**Modified Borg Dyspnea Scale:** Study subjects will be asked to rate their dyspnea symptoms daily to record their perceived shortness of breath.

**Blood Sampling**: Blood samples will be drawn as part of this study. Arterial blood gas samples will only be obtained for patients with an indwelling arterial line. Placement of an Aline is not a requirement for the study, but likely standard of care (SOC) for this patient population. The blood samples will be collected the day prior to voxelotor administration, on study day 1 - 5, and on the 2 wash out days following voxelotor administration. Blood will be collected and sent to a core laboratory for measurement of erythropoetin levels (for evidence of renal medullary hypoxia), drug trough level measurement via pharmacokinetics (PK), and P50. Local lab will be used for Hematology and Chemistry. A total of 109 mls of blood will be collected for this study.

See Schedule of Activities Table 2.

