## 3.2 Primary Study Endpoints

The primary outcome will be change in S/F ratio from baseline to 2 days after initiation of Voxelotor treatment.

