# 4 Subject Selection and Withdrawal

#### 4.1 Inclusion Criteria

- 1. Oxygen dependency due to an end-stage lung disease (pre-lung transplant population) or ALI/acute lung injury (for example but not limited to primary allograft dysfunction, infectious pneumonia, aspiration, non-cardiogenic pulmonary edema). ALI will be defined as per Berlin criteria with a P/F ratio < 100 denoting severe acute respiratory distress syndrome (ARDS), < 200 denoting moderate and < 300 mild ARDS. ALI and mild ARDS are considered synonymous. In the event of inability to obtain arterial blood gas analysis to calculate a P/F ratio, we will consider a range of patients requiring standard nasal cannulae flowing at 6 LPM (liters per minute) to maintain SaO2 > 90% as ALI, and Salter High -Flow nasal cannulae at 12-15 LPM in order to maintain SaO2 > 85% as severe ARDS.
- 2. At least 48 hours of stable, increased oxygen requirement or ventilatory support prior to the start of drug administration if consented.

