## 5.8 Blinding of Study Drug

This is an open –label study and subjects will not be randomized. There is no blinding.

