#### 7.2 Statistical Methods

Descriptive statistics for patient characteristics and baseline factors will be presented as median and interquartile range for continuous variables and number and percentage for categorical variables. The primary outcome will be change in S/F ratio from baseline to 2 days after initiation of voxelotor treatment, and the secondary outcome will be change in S/F ratio from baseline to 5 days after initiation of voxelotor treatment. Each will be compared using the Wilcoxon Signed Rank test. The baseline value will be defined as the median S/F ratio measurement during the 48-hour period before initiation of voxelotor treatment. Similarly, the

\*only if feasible/ ambulatory patients only. Exercise protocol is SOC and data collected will be reviewed from medical record.

day 2 and day 5 S/F ratio values will be defined as the median S/F ratio measurement on the second and fifth days after initiation of treatment.

All S/F ratio values will also be analyzed using a mixed-effects model with a random intercept for each patient and time in hours (relative to initiation of voxelotor treatment) as a fixed effect. Quadratic and cubic terms for time will also be included to allow for flexible modeling of treatment effect over time. We will tabulate and report all observed adverse events occurring during this trial.

For the ALI group with an arterial line in place, the PaO2/FiO2 (P/F) ratio will also be compared in a similar manner to identify whether any improvement in S/F ratio is due to clinical improvement of ALI, as reflected in the P/F ratio. The concept of Voxelotor use is an improvement in the S/F ratio (the result of left-shift in p50) for a given P/F ratio (the result of pulmonary function limiting PaO2). This may be especially important for the ALI sub-study cohort, as ALI could improve during the 5 day dosing period. Realistically, however, such progress is typically slow and, in contrast, the end-stage lung disease cohort would not be expected to improve and S/F ratio alone would reflect voxelotor effect without the need to track P/F ratios.

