## 8.4 Stopping Rules

To provide a complete safety review of each patient, participants will be enrolled and end study participation before the next subject is enrolled. This will be done for the first five participants. For the remaining 15 participants, when an SAE occurs with a subject, enrollment of new participants will pause until the SAE is completely review by the PI. After three unexpected, related SAEs are reported in this study, the enrollment of new participants will be halted.

When an unexpected rate of expected SAEs occurs, the enrollment of new participants will be halted.

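### The primary S/F ratio is read wherever unblinded staff stop the wean near 88%, so a systematic 1 to 2 point difference between baseline and Day 2 could bias the effect estimate

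*Combined protocol and SAP*

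**What the plan says.** All places are in the combined protocol and SAP.

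- **Measurement (3.1 General Design).** FiO2 is lowered slowly until the SpO2 "measurement is approximately 88" percent, and S/F is calculated there. The stated purpose is a more precise comparison. The maneuver is done by "qualified and delegated study staff or medical team". No tolerance, step size, hold time or repeat-reading rule is given. Section 6 lists only that S/F is calculated each day.
- **Design (5.3, 5.8).** Single arm, open label: "There is no blinding".
- **Endpoint (3.2).** "The primary outcome will be change in S/F ratio from baseline to 2 days after initiation of Voxelotor treatment".
- **Analysis (7.2).** "The baseline value will be defined as the median S/F ratio measurement during the 48-hour period before initiation of voxelotor treatment"; Days 2 and 5 also use medians. "Each will be compared using the Wilcoxon Signed Rank test". A mixed model on all S/F values is added. P/F is compared only in ALI patients with an arterial line; for end-stage lung disease, S/F alone is to carry the drug effect.
- **Size (7.1, 8.4).** A pilot meant to supply an effect size for a later study. No expected effect, SD or power is stated. Five patients are treated one at a time, then "For the remaining 15 participants" a different enrolment rule applies, so N is 20.
- **Eligibility (4.1).** When no blood gas is available, patients on "Salter High -Flow nasal cannulae at 12-15 LPM" to hold SaO2 above 85% count as severe ARDS.

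**The concern.** S/F depends on the SpO2 at which it is read. The actual SpO2 enters the numerator, but FiO2 need not fall in proportion, so two readings from the same lungs on the same day can differ simply because one wean ended at 90% and the other at 87%. The people who end it know whether the patient is on drug, and no control arm would cancel a shift in practice between baseline and Day 2. Any such shift goes into the primary estimate and on into the planning of the later study.

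The eligibility fallback raises a related problem. A patient who starts at or below 88% cannot be titrated down to it, and the plan does not say what S/F is recorded that day. That reading would come from a different point on the dissociation curve from the patient's other days.

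**Working it through.** The plan states no effect size, SD, alpha or p50 shift, so there is no figure of its own to reproduce. The check asks how far S/F moves when the stop is not 88%, and sets that against the S/F change from a fall in p50.

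**Inputs from the plan:** target SpO2 88%, N = 20, within-patient change, Wilcoxon signed-rank test.

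**Assumed inputs:** Hill curve with exponent 2.7 and p50 26.7 mmHg; PaCO2 term 50 mmHg; inspired pressure factor 713 mmHg; for shunt, Hb 12 g/dL and arteriovenous O2 difference 4.5 mL/dL; two-sided alpha 0.05.

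**Step 1: PaO2 at each stop.** PaO2(s) = 26.7 × (s/(1−s))^(1/2.7). This gives 52.3, 54.0, 55.8, 57.9 and 60.2 mmHg at 86%, 87%, 88%, 89% and 90%.

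**Step 2: S/F relative to an 88% stop, under three models.**

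- *A, constant P/F.* S/F is proportional to s/PaO2(s). At 86%: (0.86/52.30)/(0.88/55.85) − 1 = +4.4%. A p50 fall of d scales S/F by 1/(1−d); for 10%, 1/0.9 − 1 = +11.1%.
- *B, constant A-a gradient.* FiO2 = (PaO2 + gradient + 50)/713. If FiO2 is 0.6 at 88%, the gradient is 0.6 × 713 − 50 − 55.85 = 322. At 86%, FiO2 = (52.3 + 322 + 50)/713 = 0.595, so (0.86/0.595)/(0.88/0.6) − 1 = −1.5%.
- *C, fixed shunt q.* Arterial content Ca = 1.34 × 12 × s + 0.003 × PaO2. End-capillary content = Ca + 4.5 × q/(1−q). Solve the Hill curve for the alveolar PO2 with that content; FiO2 = (alveolar PO2 + 50)/713. At q = 0.30, FiO2 is 0.208, 0.252 and 0.340 at 86%, 88% and 90%.

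| Model | 86% | 87% | 89% | 90% | 10% p50 fall, read at 88% |
|---|---|---|---|---|---|
| A | +4.4% | +2.3% | −2.5% | −5.2% | +11.1% |
| B, FiO2 0.4 | −1.0% | −0.5% | +0.4% | +0.7% | +2.0% |
| B, FiO2 0.8 | −1.7% | −0.8% | +0.8% | +1.5% | +1.0% |
| C, shunt 20% | +4.9% | +2.7% | −3.3% | −7.5% | +6.3% |
| C, shunt 30% | +18.3% | +10.1% | −11.9% | −24.3% | +6.0% |
| C, shunt 35% | +35.8% | +17.0% | −13.8% | −24.7% | +2.9% |

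At 20% shunt the 88% point falls at FiO2 0.178, below room air (0.21), so such a patient could not be weaned to it. The low end of the shunt range therefore describes patients who would stay above 88% on room air.

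**Step 3: effect on the test.** Under model A the slope is −0.0238 in log S/F per SpO2 point. The Wilcoxon test was simulated with N = 20 and no drug effect, 600 runs per cell, for an assumed SD of all other variation in log S/F change. The table gives the rejection rate; brackets add random stop error of SD 1.5 points at each reading.

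| Other SD | No drift | Day 2 stop 1 point lower | Day 2 stop 2 points lower |
|---|---|---|---|
| 0.05 | 4% (3%) | 51% (31%) | 97% (80%) |
| 0.10 | 6% (5%) | 18% (13%) | 51% (46%) |
| 0.15 | 7% (5%) | 9% (9%) | 27% (21%) |
| 0.20 | 6% (4%) | 8% (7%) | 18% (16%) |

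In the other direction, with a true +10% effect and SD 0.10, power falls from 98% to 84% if Day 2 stops are 1 point higher and to 49% if 2 points higher. Random stop error alone lowers it only to 96%.

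**The case against.** **Random differences.** A reader might infer that everyday variation in the stop can create a positive result. It cannot: with no drift, rejection stays at 3% to 7%. A false effect needs a same-direction difference across patients. Open-label conduct makes that possible, but nothing in the documents shows that it occurs.

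**Size.** A reader might also quote a false gain of +10% to +64%. That describes a 4-point swing, baseline stopped at 90% and Day 2 at 86%. The lower figure is model A; the upper comes from one shunt case (30%, Hb 10, S/F 210 to 345). Model B gives about −2% to −3% for the same swing: (1 − 0.0104)/(1 + 0.0072) − 1 = −1.7% and (1 − 0.0166)/(1 + 0.0149) − 1 = −3.1%. So +10% to +64% is one set of assumptions and not the range, and even the sign depends on the model. A large p50 fall, 20% to 30%, gives +25% to +43% in model A and would survive a 1 to 2 point drift there.

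**Safeguards.** Daily core-laboratory P50, medians, the mixed model and arterial-line P/F all help interpretation. None corrects the bias. P50 confirms the left shift without adjusting S/F, and medians and the mixed model carry a systematic shift through. P/F comes from routine care, not necessarily at the weaned FiO2, and 7.2 does not rely on it for end-stage lung disease.

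**Eligibility.** The 85% figure is a fallback severity label. It does not say that patients sit between 85% and 88%, only that some may; the number is unknown.

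**Conclusion.** The point holds in a limited form. The stop is undefined, the operators are unblinded and no control arm would cancel a drift. A systematic 1 to 2 point difference between baseline and Day 2 could shift S/F by under about 2% with reversed sign (constant A-a gradient), about 2% to 5% (constant P/F), or roughly 3% to 36% (shunt 20% to 35%). Against an assumed 10% p50 fall, worth about +1% to +11% in the same models, that can rival a modest drug effect.

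Every size here rests on assumed gas exchange, Hb, p50 shift and SD. The documents can settle neither how sensitive S/F is in these patients nor whether any drift will occur. What they do settle is that the plan gives no means of detecting or correcting one.

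**What to change.** - Record the SpO2 and FiO2 pair at each step of the existing maneuver, using the same step and hold procedure at baseline and on drug.
- Define the primary S/F as 88 divided by the FiO2 at SpO2 88%, interpolated or fitted from the recorded pairs by a rule fixed in advance. Do not require more desaturation than the protocol already specifies.
- Report the SpO2 actually reached beside each S/F value.
- Flag days when 88% is not bracketed, whether the patient starts at or below 88% or remains above it on room air. State what value those days contribute, and repeat the primary analysis without them. That repeat is a sensitivity check only: patients above 88% on room air are likely to be among the best oxygenated, so the flagged days are not a random subset.

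The cost is a few more recorded values per maneuver, some SAP wording and some flagged days. Steps that are not recorded cannot be recovered later. Interpolation reduces operator influence but does not remove it, because the same unblinded staff still run the wean.
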